7.2 Statistical Methods

The primary outcome is spontaneous preterm birth before 34 weeks of gestation. Secondary outcomes include gestational age at delivery, interval between diagnosis and delivery, birth weight, spontaneous preterm birth rates at less than 24, 28, 32 and 37 weeks gestation, clinical chorioamnionitis and spontaneous rupture of membranes at less than 34 weeks gestation. Secondary safety outcomes include admission to NICU, neonatal death, length of stay in the NICU until discharge home, composite adverse neonatal outcome that includes necrotizing enterocolitis, intraventricular hemorrhage (grade 2 or higher), respiratory distress syndrome, retinopathy of prematurity and treatment for sepsis), and significant adverse maternal effects will include: intraoperative rupture of membranes, chorioamnionitis, postpartum hemorrhage (estimated blood loss and requirement of blood transfusion, cervical tear and uterine rupture).

Statistical analysis will be based on the intention-to-treat principle.

Comparisons between the two groups will be made with the Mann-Whitney U test. Univariate comparisons of dichotomous data will be performed with Fishers exact test. The p values for all hypotheses will be two sided, and p values of less than 0.05 will be considered to be significant. The risk of spontaneous preterm birth before 34 weeks will be quantified by use of the relative ratio and 95% CI. Multivariate analysis will be performed using logistic regression. The risk of spontaneous preterm birth from randomization until 34 weeks will be assessed with Kaplan-Meier analysis, in which gestational age

is the timescale, spontaneous delivery is the event, and elective deliveries are censored. SPSS software package (version 16.0) will be used for all statistical analyses.

8 Safety and Adverse Events

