1.2 Clinical Data to Date

A retrospective review of 12 women with twin pregnancies who underwent a physical exam-indicated cerclage (dilated cervix on examination or membranes visible at the external cervical os on speculum examination) during the second trimester were compared with 31 singleton pregnancies undergoing the same procedure from 1997 to 2012.²⁵ Comparing twins to singletons, the median time from cerclage placement to delivery was similar (92 vs. 106 days, p=0.3), as was the median GA at delivery (33.5 vs. 35.0 weeks, p=0.2). The likelihood of delivery at >32 weeks (75.0% vs. 71.0%, p>0.9) and the likelihood of neonatal survival to discharge (83.3% vs. 83.9%, p>0.9) were also similar. A case report of 4 women with twin pregnancy and cervical dilation with bulging membranes gave birth on an average of 48.5 days after cerclage placement.²⁶ A more recent publication evaluated 104 women with twin pregnancy vs. 334 singleton pregnancies with dilated cervix, median gestation at delivery was (31.9 weeks vs. 32.7 weeks) and delivery before 28 weeks (33.7% vs. 35.8%, P = .69) respectively.²⁸ **None of these publications have had an appropriate control group: twin gestation with expectant management.** Only one small retrospective cohort study had a control group with expectant management,²⁷ 23 women were identified with twin pregnancy, cervical dilation and visible membranes between 16-24 weeks; 16 underwent physical exam indicated cerclage while 7 received expectant management (control). In the control group 50% of the women were delivered prior to 24 weeks. Interval from time at diagnosis to delivery was significantly prolonged by approximately 6.8 weeks in the cerclage group, they had significant decreased SPTB ≤28 weeks (31.2% vs. 85.7% p=0.02) and increased neonatal survival upon discharge 71.8% vs. 42% (p=0.1).

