3.3 Secondary Study Endpoints

Secondary effectiveness endpoints:

- Gestational age at delivery
- Interval between diagnosis and delivery
- Birth weight of each neonate
- Spontaneous preterm birth rates at less than 24, 28, 32 and 37 weeks gestation
- Spontaneous rupture of membranes before 34 weeks gestation

Secondary safety endpoints:

- Admission to the NICU and length of stay
- Neonatal death before discharge
- Composite adverse neonatal outcome (includes necrotizing enterocolitis, Intraventricular hemorrhage (grade 2 or higher), respiratory distress syndrome, retinopathy, treatment for sepsis and neonatal death)
- Chorioamnionitis (clinical or histological)
- Significant adverse maternal effects including intraoperative rupture of membranes, bleeding and cervical laceration (tear).

4 Subject Selection and Withdrawal

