4.1 Inclusion Criteria

1. Pregnant women more than 18 years of age
2. Diamniotic twin pregnancy (limits the participants to female gender)
3. Asymptomatic
4. Cervical dilation 1- 5 cm and/or visible membranes by pelvic exam or speculum exam on second trimester ultrasound between 16-23 6/7 weeks gestation

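### The composite adverse neonatal outcome includes neonatal death in section 3.3 but not in 7.2, and neither section names the infant denominator or says how fetal losses count

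*Combined protocol and SAP*

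**What the plan says.** The plan defines this secondary safety endpoint twice.

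- **Section 3.3** gives six components; its list closes with "retinopathy, treatment for sepsis and neonatal death".
- **Section 7.2** gives five: a "composite adverse neonatal outcome that includes necrotizing enterocolitis, intraventricular hemorrhage (grade 2 or higher), respiratory distress syndrome, retinopathy of prematurity and treatment for sepsis". Death is not among them.

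Both sections also carry neonatal death as an outcome of its own; in 3.3 it reads "Neonatal death before discharge". The secondary objective in 2.2 covers neonatal illness and death together.

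On the analysis set, 7.2 says only "Statistical analysis will be based on the intention-to-treat principle". It assigns Fisher's exact test to dichotomous data without saying whether the unit is the mother or the infant. Section 3.3 specifies a per-infant measure for birth weight alone. Section 6.5 sets the collection window, which runs to discharge home. Fetal death appears only in the list of reportable events in 8.2, and only when attributed to the cerclage.

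**The concern.** Death competes with every diagnosis in the composite: an infant who dies early cannot later be given one. If death is not itself a component, such an infant can be scored as free of an adverse outcome. The arm with more early deaths then gains on an endpoint meant to show harm.

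Early loss is a realistic prospect here. Enrolment opens at 16 weeks, and spontaneous birth before 24 weeks is a listed endpoint. Of the one cited twin cohort with expectantly managed controls, section 1.2 says: "In the control group 50% of the women were delivered prior to 24 weeks". It does not say how many of those deliveries were live births.

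Adopting the 3.3 list would settle the components but not the denominator. The intention-to-treat sentence fixes which women are analysed, not which of their fetuses or infants are counted. The trial is open-label, so a rule left open could be chosen once results are known. NICU admission and length of stay share the problem in a minor way, because an infant who dies before admission adds no admission and no days.

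**Working it through.** **1. Text.** The two lists agree on five morbidities and differ only in neonatal death. The separate listing of neonatal death does not show which composite is meant, because it appears in both sections. No rule in the document gives one section precedence.

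**2. The plan's own figure.** There is none for this endpoint. The one design figure, for the primary outcome (7.1), reproduces: 80% vs 40%, two-sided 5%, 80% power, normal approximation without continuity correction gives 23 per arm, 46 in total; 46/0.90 = 51.1, rounded up to 52. Nothing below changes it.

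**3. Illustration: inputs.**

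- Survival to discharge S: 0.718 cerclage, 0.42 expectant (section 1.2; 16 vs 7 women, p=0.1). *Assumed* to be per fetus. Deaths d = 1 − S: 0.282 and 0.58.
- m, morbidity among survivors: *assumed* 60% in both arms.
- q, share of neonatal deaths with a listed morbidity recorded: *assumed*, varied from 0 to 100%.
- f, share of deaths that are fetal: *assumed* 0 unless stated.

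**4. Formulas.** Over all fetuses:

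- 7.2 list: S·m + d(1−f)·q
- 3.3 list: S·m + d(1−f)
- every fetal or neonatal death counted: S·m + d

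For live births, divide the first two by S + d(1−f).

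**5. Results with f = 0, m = 60%.**

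| Composite | Cerclage | Expectant | Ratio |
|---|---|---|---|
| 7.2, q = 0 | 0.718×0.6 = 43.1% | 0.42×0.6 = 25.2% | 1.71 |
| 7.2, q = 30% | 51.5% | 42.6% | 1.21 |
| 7.2, q = 60% | 60% | 60% | 1.00 |
| Death counted | 43.1 + 28.2 = 71.3% | 25.2 + 58 = 83.2% | 0.86 |

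With equal m and q = 0, the 7.2 ratio is 0.718/0.42 = 1.71 whatever m is. With death counted it is 0.76 at m = 40% and 0.93 at m = 80%. With a smaller assumed survival gap (65% vs 50%, m = 60%, q = 0), the 7.2 composite is 39% vs 30% (1.30), and 74% vs 80% with death counted.

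**6. Where the reversal ends.**

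- At q = m, here 60%.
- At q = 0 over all fetuses, when cerclage-survivor morbidity is below 0.42/0.718 = 58% of the expectant rate.
- At q = 0 over live births with f = 50%, the limit is (0.42/0.71)/(0.718/0.859) = 71%; with f = 75% it is (0.42/0.565)/(0.718/0.7885) = 82%.
- If survivor morbidity halves, matching the 80% to 40% ratio in 7.1 (30% vs 60%): 0.718×0.3 = 21.5% vs 25.2%, ratio 0.86 over all fetuses. Over live births with f = 50%: 0.2154/0.859 = 25.1% vs 0.252/0.71 = 35.5%, ratio 0.71. There is no reversal in either.

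**7. Denominator alone (m = 60%, f = 50%).** The 3.3 list over live births gives 66.6% vs 76.3% (0.87). Keeping fetal losses in the denominator but scoring them as non-events gives 57.2% vs 54.2% (1.05). Counting every death over all fetuses gives 0.86. With f = 100%, the 7.2 list over live births gives 60% vs 60%.

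**The case against.** The strongest reply is that 3.3 is the endpoint section and 7.2 only restates it, in open-ended wording and with a stray bracket. The objective in 2.2 joins death to disease, so the intent is reasonably clear. This stands as a reading of intent, and the omission is probably a slip. It does not tell the analyst which list to program.

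Second, the reversal depends on equal survivor morbidity, which sits badly with the trial's own hypothesis. That is right: halving morbidity removes it. The survival inputs are also weak. They come from 16 and 7 women, carry no stated denominator, and sit beside a 50% figure that cannot be a count of 7 women (0.5×7 = 3.5). The 1.05 result needs an artificial rule under which fetal losses are in the denominator but are not events; on a plain live-birth reading the 3.3 list gives 0.87.

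A reader might infer that 7.2 removes neonatal death from the trial's results. It does not, because neonatal death stays a separate outcome. A reader might equally infer that separate reporting keeps all deaths in view. That fails for fetal deaths: gestational age at delivery and birth before 24 weeks reflect them only indirectly, and the list in 8.2 covers only those attributed to cerclage.

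**Conclusion.** The point holds as a conflict between two definitions, together with an unstated denominator and an unstated rule for fetal loss. It should be fixed, and it is confined to one secondary safety endpoint.

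The textual finding is firm. The size is not: the move from 1.71 to 0.86 is a corner case that rests on per-fetus survival of 71.8% vs 42%, equal 60% survivor morbidity, all deaths neonatal, and none with a recorded morbidity. A reader might take it as a forecast that the composite will favour expectant management. The documents do not support that, since they give no survivor morbidity, no split between fetal and neonatal deaths, and no share of dying infants with a diagnosis. The illustration shows only that the definition can decide the direction of the result.

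**What to change.** Use the 3.3 component list, including death, in both sections. Count fetal and neonatal deaths from randomisation to discharge, over all fetuses of randomised women with known outcome, and give the number with unknown outcome by arm. That is 52×2 = 104 fetuses with complete follow-up, or 46×2 = 92 if the planned loss occurs. A live-birth denominator is also acceptable if stated in advance with fetal losses by arm shown beside it.

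Report every component separately, and show NICU admission and stay alongside deaths. If the fetus or infant is the unit, use an analysis that allows for twin pairs; plain Fisher's test does not.

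The cost is wording in 3.3 and 7.2. Section 6.5 already provides for abstracting pregnancy and neonatal outcomes to discharge, so what is needed is that each fetus's outcome is recorded. No extra subjects or visits are required. The downside is that the composite mixes death with morbidity, and that counting fetal deaths makes it a perinatal rather than a purely neonatal measure, which is why the components must be shown.

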1.3 Risk/Benefits

Major risks of physical exam indicated cerclage that have been reported in previous studies involving singleton pregnancies and include intraoperative rupture of membranes between 4% and 15%, cervical laceration, bleeding, chorioamnionitis (undiagnosed at the time of cerclage or acquired posteriorly to its placement due to exposed membranes into the vaginal flora), failure to place the cerclage due to advanced cervical dilation and failure of the cerclage on prolonging pregnancy with possible pregnancy loss or delivery at a perivable gestational age around 23-26 weeks of gestation.^{23, 24, 29-32} Other risks of cerclage are those associated with anesthesia during the surgical procedure: hypotension, allergy to medications, post spinal headache. After the cerclage placement other risks maybe present during the following weeks as preterm contractions with the cerclage in place may cause laceration of the cervix and bleeding or preterm premature rupture of membranes in which case the cerclage needs to be removed.

Minor side effects include increased noninfectious vaginal discharge: there is a theoretical disruption the vaginal flora associated with foreign object, and minimal discomfort at the time of cerclage removal.

The potential benefits include prolongation of pregnancy, decreasing very preterm delivery (< 28 weeks), very low birth weight (<1500 grams), low birth weight (<2500 grams) and decreased neonatal morbidity (admission to the intensive care unit, respiratory distress, need of intubation, necrotizing enterocolitis, intraventricular hemorrhage), neonatal mortality and long term disease or disability associated with prematurity. These potential benefits are based on results of previous retrospective cohorts of available research in singletons and case reports in twin pregnancies. These benefits significantly outweigh the risk of having a complication related to cerclage placement.

Measurement to decreased risks associated to the cerclage: All of the investigators have received formal training on physical exam indicated cerclage placement. The training and experience of the investigators will minimize the risks associated with cerclage placement.

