1. Maternal sepsis with admission to ICU attributable to the cerclage placement
2. Maternal death attributable to the cerclage placement
3. Maternal bleeding requiring blood transfusion attributable to cerclage placement
4. Fetal and/or neonatal death or injury attributable to the cerclage placement

Frequency of monitoring reports: after approximately 50% of the subjects have delivered

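### Sections 3.3 and 7.2 define the maternal safety outcome differently, and the 7.2 list names no operative or antepartum bleeding

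*Combined protocol and SAP*

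**What the plan says.** Section 3.3 (Secondary Study Endpoints) lists, among the safety endpoints, "Significant adverse maternal effects including intraoperative rupture of membranes, bleeding and cervical laceration (tear"). Bleeding carries no time window there, and laceration is an item of its own. Chorioamnionitis is a separate safety endpoint in the same list: "Chorioamnionitis (clinical or histological").

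Section 7.2 (Statistical Methods) restates the outcome: "significant adverse maternal effects will include: intraoperative rupture of membranes, chorioamnionitis, postpartum hemorrhage". The hemorrhage item then continues with a bracket: "postpartum hemorrhage (estimated blood loss and requirement of blood transfusion, cervical tear and uterine rupture"). Section 7.2 also names clinical chorioamnionitis among the other secondary outcomes.

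Section 1.3 (Risk/Benefits) describes the harms expected from the procedure. The major risks include "intraoperative rupture of membranes between 4% and 15%, cervical laceration, bleeding, chorioamnionitis". For the weeks after placement it adds that "preterm contractions with the cerclage in place may cause laceration of the cervix and bleeding". The reportable events under the stopping rules in Section 8.2 include "Maternal bleeding requiring blood transfusion attributable to cerclage placement".

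**The concern.** The endpoint section and the analysis section give two different lists for one safety outcome. In moving from 3.3 to 7.2, the general term for bleeding becomes bleeding after delivery, and cervical tear moves from standing alone to a place inside the hemorrhage bracket. Uterine rupture appears only in 7.2, and chorioamnionitis changes position.

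What is at stake is which women count as having a maternal harm event. Section 1.3 places the bleeding risk of cerclage at surgery and in the following weeks. An analyst who builds the safety table from 7.2 would tabulate bleeding after delivery by arm and would have no instruction to compare bleeding at or after placement. The trial is open-label, so a list left unsettled could be settled by people who know the allocation and the events.

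**Working it through.** The plan states no figure on this point, so there is none to reproduce. The check is a comparison of the texts, followed by a statement of scale.

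**Step 1. Component by component.**

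| Component | Section 3.3 | Section 7.2, bracket read literally | Section 7.2, bracket closed after transfusion |
|---|---|---|---|
| Intraoperative rupture of membranes | named | named | named |
| Bleeding at placement | covered (bleeding, any time) | not named | not named |
| Antepartum bleeding | covered (bleeding, any time) | not named | not named |
| Postpartum hemorrhage | covered (bleeding, any time) | named | named |
| Cervical laceration | own item | within postpartum hemorrhage | own item |
| Uterine rupture | not named | within postpartum hemorrhage | own item |
| Chorioamnionitis | separate safety endpoint | maternal effect | maternal effect |

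Moving the bracket changes the rows for laceration and uterine rupture. It does not change the two rows for bleeding before delivery. That gap comes from the choice of term, not from punctuation.

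**Step 2. Two cases.**
- A woman bleeds at placement at 20 weeks and is transfused, with no hemorrhage at delivery. She has a bleeding event under 3.3 and, if the bleeding is judged attributable to placement, a reportable event under 8.2. She matches no bleeding item in 7.2.
- A woman has a cervical tear without postpartum hemorrhage. She is an event under 3.3. Under 7.2 she is an event only if the bracket is a slip.

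**Step 3. Is the bracket a reliable guide?** Probably not. Earlier in the same sentence the neonatal composite ends at "retinopathy of prematurity and treatment for sepsis" with a closing bracket that was never opened. The literal reading would also make uterine rupture a part of hemorrhage, which is hard to believe was meant.

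**Step 4. Where else is bleeding captured?**
- Section 8.3 requires all adverse effects in the study period to be recorded.
- Appendices 1 and 2 ask about vaginal bleeding, yes or no, without severity.
- Section 8.2 covers bleeding only if it is transfused and attributed to placement, so it has no counterpart in the expectant arm.
- Section 8.5.1 provides one board review of safety data, after about 50% of subjects have delivered.

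These are recording and monitoring. None of them specifies a final comparison between arms.

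**Step 5. Scale.** Section 7.1 gives 26 women per arm. One woman reclassified moves an arm's rate by 1/26 = 3.8 percentage points, and two move it by 2/26 = 7.7 points. The documents give no rate for operative or antepartum bleeding. If 2% to 10% of the cerclage arm had such bleeding (an assumption), that would be 0.02 × 26 = 0.52 to 0.10 × 26 = 2.6 women whom 3.3 counts and the 7.2 list does not name.

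**The case against.** The strongest reply is that nothing is lost. No text says that 7.2 overrides 3.3, and bleeding and laceration remain endpoints under 3.3. The opening of the 7.2 list does not declare it closed, and 7.2 applies Fisher's exact test to dichotomous data generally, so bleeding under 3.3 could be compared without further text. The list also keeps intraoperative rupture of membranes, which belongs to the operated arm and is the only one of these harms with a rate in the documents (4% to 15%). The laceration difference may be only punctuation.

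Most of this stands, and it rules out several stronger readings that a reader might infer:

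- *That 7.2 analyses only postpartum hemorrhage as maternal harm.* This is true of bleeding alone, since membrane rupture and chorioamnionitis are also listed.
- *That bleeding from cerclage disappears from the trial.* It is absent from the named 7.2 list, but it is recorded, asked about and partly monitored.
- *That the plan has decided to count tears only with hemorrhage.* The unmatched bracket in the same sentence makes a slip more likely than a decision.
- *That the comparison is tilted toward finding cerclage safe.* Suppose 10% of each arm has postpartum hemorrhage and a further 2% to 10% of cerclage women bleed earlier, in different women. Then 3.3 shows 12% to 20% against 10%, and 7.2 shows 10% against 10%. Every rate here is assumed, and the contrast also needs no earlier bleeding at all in the expectant arm. If a share c of that arm bleeds before delivery, the gap of x = 2 to 10 points becomes x − c, and it vanishes when c = x. Interim contacts ask about vaginal bleeding in both arms. Bleeding around delivery may itself be partly due to the cerclage, given the laceration mechanism in 1.3.

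What the reply does not remove is the conflict. If the 7.2 list is open, the make-up of a safety endpoint in an open-label trial is undecided. If it is closed, it leaves out bleeding that 3.3 includes.

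**Conclusion.** The point holds as an inconsistency that changes who counts as a maternal harm event. Section 3.3 includes bleeding at any time and laceration separately. Section 7.2 names postpartum hemorrhage as the only bleeding component and leaves the status of cervical tear and uterine rupture ambiguous. The omission of operative and antepartum bleeding from 7.2 does not depend on how the bracket is read; the laceration difference does.

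The size of the effect is unknown, because the documents give no rates. The scale is one or two women per arm, each worth 3.8 percentage points; the 2% to 10% range is an assumption and serves only as illustration. An effect in favour of cerclage is plausible mainly for operative bleeding, because the expectant arm has no placement surgery. For antepartum bleeding the direction is uncertain. The primary outcome and the sample size are not affected. The definitions should be reconciled before safety data are tabulated by arm.

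**What to change.** Use one list in 3.3 and 7.2. Count each component separately, in both arms, from randomisation to maternal discharge, which fits the collection window in Section 6.5:

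- intraoperative rupture of membranes;
- operative or antepartum bleeding, with transfusion as a flag;
- postpartum hemorrhage;
- cervical laceration;
- uterine rupture.

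Close the hemorrhage bracket so that laceration and uterine rupture stand outside it. Put chorioamnionitis in the same place in both sections, with the same definition (clinical, or clinical and histological). State the time window of each bleeding item and that the list is complete.

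The cost is small: wording in two sections and matching case report form fields. One check is needed. Section 4.3, item 10, names prenatal visits, ultrasound reports, labor and delivery, and newborn outcomes as the records to be obtained, but not operative or cerclage-removal records. Removal may take place in the primary physician's office, so abstraction from those two sources should be confirmed or added. Treatment and sample size do not change.

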6.5 Pregnancy Outcome

After subjects have delivered, information regarding outcome of the pregnancy and neonatal outcome until mother and neonate are discharge home. The information will be abstracted from the subjects'

medical records. A release of medical records consent will be signed at the time of randomization, in case the patient delivers at an outside institution.

7 Statistical Plan

1. This is a multi-center, open-label, randomized study
2. Subjects will be randomized in a 1:1 fashion to either receive the cervical cerclage, or standard obstetric management
3. Method for assigning subjects to treatment groups: A computer-based system will be used for the randomization assignments. Subjects will be randomized using blocks of randomly varying size (e.g., 2, 4 and 6).

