7.1 Sample Size Determination

Calculation of sample size was based on a reduction in the incidence of spontaneous delivery before 34 weeks from 80% in the expectant management group to 40% in the cerclage group, with a power of 80%. To detect this difference at a significance level of 5%, we will need to enroll a total of 46 subjects with 23 subjects in each arm, plus 10% for loss of follow up. Total 52 subjects with 26 subjects in each arm

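### Neonatal secondary outcomes: section 7.2 states no unit of analysis and makes no allowance for twin pairing, although every method it offers assumes independent observations

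*Combined protocol and SAP*

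**What the plan says.** **Who is randomised.** The opening list of section 7 says "Subjects will be randomized in a 1:1 fashion to either receive the cervical cerclage, or standard obstetric management", and section 7.1 gives "Total 52 subjects with 26 subjects in each arm". Section 4.1 admits only diamniotic twin pregnancies, so the two neonates of a woman are always in the same arm.

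**What is measured on neonates.** Section 3.3 lists "Birth weight of each neonate" and "Admission to the NICU and length of stay", followed by neonatal death and a composite of neonatal morbidity. Section 2.2 makes NICU use and neonatal disease or death a secondary objective. Section 7.2 repeats these outcomes, with birth weight no longer described as per neonate.

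**How they are tested.** Section 7.2 says "Comparisons between the two groups will be made with the Mann-Whitney U test" and "Univariate comparisons of dichotomous data will be performed with Fishers exact test". It adds multivariable logistic regression without naming an outcome, and "The p values for all hypotheses will be two sided, and p values of less than 0.05 will be considered to be significant". Its Kaplan-Meier analysis concerns delivery and is not a method for neonatal outcomes.

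**What is not there.** Neither 7.2 nor any other section says whether a neonatal outcome is counted per neonate or per pregnancy, how two twins are combined into one value, or how correlation within a pair is handled.

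**The concern.** Twins share one pregnancy and, as a rule, nearly the same gestational age at birth, so their outcomes are correlated. Mann-Whitney, Fisher's exact test and ordinary logistic regression treat each row as independent. With neonates as rows, the plan's 26 women per arm become 52 observations per arm that hold less information than 52 independent ones. P values come out too small, and a neonatal benefit or harm would be declared more often than the stated 5%.

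There is a second risk. At least three countings fit the text: each neonate, any affected twin per pregnancy, and twin A and twin B separately. They can give different p values. In an open-label trial, a unit left unstated can be settled after the data are seen.

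**Working it through.** **1. The plan's own figure.** Section 7.1 assumes 80% versus 40%, two-sided 5%, power 80%. With the pooled two-proportion formula:

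n per arm = [1.960·√(2·0.6·0.4) + 0.842·√(0.8·0.2 + 0.4·0.6)]² / 0.4² = (1.358 + 0.532)² / 0.16 = 22.3, so 23.

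That is 46 women; 46/0.9 = 51.1, so 52. The stated size reproduces. It is per woman for a per-woman outcome and needs no pairing allowance.

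**2. Inputs for the neonatal outcomes.** From the documents: pairs of two, two-sided 0.05, 26 women enrolled and 23 evaluable per arm. Assumed, because the documents give none: ICC of 0.2, 0.5 and 0.9, and the event rates. All error rates below are for no true effect.

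**3. Approximate size.** The variance of an arm mean over m pairs is σ²(1 + ICC)/(2m), but a test that ignores pairing uses σ²/(2m). The true level is then about 2[1 − Φ(1.96/√(1 + ICC))]:

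- ICC 0.2: 1.96/1.095 = 1.79, giving 7.4%
- ICC 0.5: 1.96/1.225 = 1.60, giving 11.0%
- ICC 0.9: 1.96/1.378 = 1.42, giving 15.5%

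The number of pairs cancels, so the result is much the same for 23 and 26.

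**4. Mann-Whitney by simulation** (normally distributed pairs, 40,000 replicates):

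| Rows in the test | ICC 0.2 | ICC 0.5 | ICC 0.9 |
|---|---|---|---|
| Neonates, 23 pairs per arm | 7.2% | 10.7% | 15.4% |
| Neonates, 26 pairs per arm | 7.1% | 10.8% | 15.7% |
| Pregnancy means, 23 or 26 per arm | 4.6–4.9% | 4.6–4.9% | 4.6–4.9% |

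A skewed (lognormal) outcome, as NICU stay may be, gives 7.3/10.7/15.3% per neonate and 4.7–4.9% on means (26 pairs).

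**5. Fisher by exact enumeration.** With event rate p, P(both affected) = p² + ICC·p(1 − p) and P(exactly one) = 2p(1 − p)(1 − ICC). For p = 0.5 and ICC 0.5 these are 0.375 and 0.25.

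| Neonates as rows | ICC 0.2 | ICC 0.5 | ICC 0.9 |
|---|---|---|---|
| 23 pairs, p = 0.50 | 4.5% | 7.4% | 11.4% |
| 26 pairs, p = 0.50 | 6.0% | 9.2% | 13.5% |
| 26 pairs, p = 0.10 | 3.2% | 5.6% | 9.6% |
| 26 pairs, p = 0.05 | 1.5% | 2.9% | 6.2% |

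Fisher starts low: with ICC 0 and p = 0.50 its level is 2.8% with 23 pairs and 3.9% with 26. At ICC 0.2 and 23 pairs it never reaches 5% for event rates from 0.10 to 0.70 (maximum 4.8%). With 26 pairs it does so only for rates from 0.36 to 0.64.

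**6. Other countings** (26 pregnancies per arm, event rates 0.10–0.70). Fisher on any affected twin: 1.2–2.8% for ICC 0.2–0.9. Rank test on the number of affected twins (0, 1 or 2): 4.7–5.2%. Separate birth-weight tests in twin A and twin B keep the level individually, but the chance that at least one is significant is 6.9–9.2%.

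**The case against.** The strongest reply is that section 7.2 prescribes nothing wrong. It compares two groups by intention to treat, and those groups are made up of randomised women. The entry in 3.3 says what is measured, not that each neonate is a separate row. No neonatal outcome is named beside either test. The same tests on one value per woman would be valid. Fisher is conservative, the ICC is assumed, and only secondary outcomes are involved.

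Much of this stands. A reader might infer that the plan commits the trial to testing neonates as independent. The documents do not support that: birth weight alone is listed per neonate, in an endpoint list, and for the rest the unit is simply open. A reader might also infer that Fisher is always inflated; step 5 shows that it is not, especially at the planned 23 evaluable per arm. Nor do the documents support extending the problem to the primary outcome or the sample size.

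What remains is that the only neonate-level wording in the plan points towards neonates as rows for birth weight, the matching test is Mann-Whitney, and that test has no conservatism to absorb the pairing. Its level exceeds 5% at every positive ICC examined. That a valid per-woman reading exists is a reason to write it down.

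**Conclusion.** The concern holds as an unspecified unit of analysis with a quantifiable consequence, not as a demonstrated wrong analysis. If neonates are tested as independent, the false-positive rate is about 7/11/15% for Mann-Whitney at ICC 0.2/0.5/0.9. For Fisher it ranges from below 5% to 13.5% over the cases in step 5, depending on ICC, event rate and number of pairs. These figures rest on assumed ICCs and event rates, complete pairs and no true effect. The finding that pregnancy-level analysis keeps the level rests on complete pairs too, or on missing twins being unrelated to arm and outcome.

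It is confined to birth weight, NICU admission, NICU stay, neonatal death and the composite. Spontaneous birth before 34 weeks, gestational age at delivery, the interval to delivery, the other pregnancy-level outcomes and N = 52 are untouched. It should be fixed before outcomes are compared, but it does not threaten the main result.

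**What to change.** In section 7.2, state that neonatal outcomes are analysed with the pregnancy as the unit or cluster, by one of two routes named for each outcome:

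- **One value per pregnancy, planned tests kept.** For example mean birth weight and mean NICU stay by Mann-Whitney; number of affected twins by Mann-Whitney, or any affected twin by Fisher.
- **Per neonate, pairing modelled.** GEE or a mixed model with a small-sample correction, since there are at most 26 clusters per arm. This must also cover any logistic regression of a neonatal outcome.

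State in advance how fetal loss and death before discharge enter each neonatal outcome. Such losses may differ by arm, and a death before discharge shortens the NICU stay, so averaging over surviving or evaluable twins is not automatically neutral. Leave the tests for maternal and pregnancy-level outcomes as they are.

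The cost is a few sentences and somewhat larger p values. For an assumed birth-weight difference of 0.8 SD and ICC 0.2/0.5/0.9, the rank test on pregnancy means has power of about 91/84/75% with 23 per arm and 94/89/81% with 26. The per-neonate test shows 97/95/93% with 26, but at the inflated error rate. Sample size and primary analysis do not change.
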